This is a prospective, observational, exposure cohort study of pregnancy outcomes in women exposed to belimumab during pregnancy compared to pregnancy outcomes in women with a diagnosis of SLE who have not used belimumab during pregnancy (but may have been exposed to other medications for the treatment of SLE) (disease comparison group). Pregnant women exposed to belimumab who do not meet the inclusion criteria of this study may be followed as part of an exposure case series. All participants will be recruited via voluntary participant registration following informed consent. Participants may withdraw from the study at any time.

Population

The study population includes pregnant women who reside in the US or Canada. Two cohorts of women will be enrolled prospectively: **1)** a belimumab-exposed cohort with exposure to at least one dose of belimumab from 3 months before the first day of the last menstrual period (LMP) to the end of pregnancy; **2)** a disease cohort with SLE who have not been exposed to belimumab from 3 months before the first day of the LMP or throughout pregnancy. Pregnant women exposed to belimumab who do not meet the inclusion criteria of this study may be followed separately as part of an exposure case series

Variables

Exposure will be defined as belimumab treatment at any time during pregnancy (from 3 months before the first day of the LMP throughout pregnancy) by maternal report and verified by medical record review, with detailed information on the gestational timing, route of administration, dose, and dates of exposure. The primary outcome variable is major birth defects. Secondary outcome variables include a pattern of minor birth defects, spontaneous abortion (including ectopic/molar pregnancy), elective termination, stillbirth, preterm delivery, SGA and infant outcomes of postnatal growth deficiencies, developmental concerns, and serious or infections in live born infants up to one year of age. These will be obtained by maternal report and verified by medical record review. Potential confounders or covariates to be collected include age, race/ethnicity, body mass

index, socioeconomic status, pregnancy and health history, lifestyle factors, comorbidities, maternal exposures (including medication, vaccine, vitamin/mineral, and illnesses), prenatal tests, infant complications and pediatric exposures, and measures of SLE disease severity (including SLE specific lab values if available).

Data Sources

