8.5. Study size

The proposed sample sizes in each of the study groups are as follows:

- 200 women exposed to belimumab at any time from 3 months prior to the first day of LMP through the end of pregnancy
- 200 women with SLE, unexposed to belimumab

An enrollment of 200 participants in each of the cohort groups is planned over 5 years. Based on previous experience with the MotherToBaby/OTIS Autoimmune Diseases in Pregnancy Project, the expected proportion of women to enroll in first trimester is approximately 70% [Chambers, 2019a]. It is estimated that participants will be an average of 7-10 weeks post-LMP at the time of enrollment. Given this mean gestational timing at enrollment, the anticipated live-birth rate is 85%, which includes a spontaneous abortion and elective abortion rate of 10% [Wilcox, 1988; Zinaman, 1996; Kanmaz, 2019; Chambers, 2019a] and an estimated lost to follow-up rate of 5% [Chambers, 2018], this will result in 170 pregnancies with at least one live born infant in each cohort at the end of recruitment. As a conservative estimate, the power calculations were also conducted assuming a live-birth rate of 80%, which includes a spontaneous abortion and elective abortion rate of 15% [Chambers, 2016], and an estimated lost to follow-up rate of 5%. This conservative estimate will result in 160 pregnancies with at least one live born infant in each cohort at the end of recruitment.

This study is designed to serve as an early warning system to identify a previously unrecognized major teratogen by identifying major birth defects in infants of exposed mothers. For less potent teratogens or for drugs and biological products that cause other adverse pregnancy outcomes, the study can function as a signal detection study and generate hypotheses that can be tested in other studies using other methods that may be better powered to assess these outcomes (FDA, 2019).

Table 4 gives the minimum detectable effect sizes with 80% power [two-sided significance level 0.05]) for the primary outcome of major birth defects. Table 4 includes

varying expected live births in each cohort, using varying rates of SAB/elective terminations and includes varying background rates of major birth defects, based on existing literature on pregnant women with SLE [Vinet, 2012; Gladman, 2010]. As a reference, the effect size has also been calculated based on the general population background rate of major birth defects of 2.8% in the Atlanta metropolitan area [CDC, 2017].

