Table 4 Risk estimates for belimumab-exposed pregnancies relative to the primary comparison group for the primary outcome; all estimates use an α -level of 0.05 and power of 0.8 (80%).

Outcome	N in Each Group*	Target Enrolled N in Each Group	Rate in Comparison Group**	Relative Risk***
Using background rates of primary outcome within SLE population				
Major birth defects	160	200	13% ^a	1.9
Major birth defects	160	200	5% ^b	2.8
Major birth defects	170	200	13% ^a	1.9
Major birth defects	170	200	5% ^b	2.7
Using background rates of primary outcome within general population as reference				
Major birth defects	160	200	3% ^c	3.5
Major birth defects	170	200	3% ^c	3.4

N= number of pregnancies with at least one live born infant

*Sample size for the first two rows of the table allows for spontaneous abortion and elective abortion rate of 15% (Chambers, 2016) and lost to follow-up rate of 5%; sample size (Chambers, 2018) for the following two rows of the table allows for spontaneous abortion and elective abortion rate of 10% (Wilcox, 1988; Zinaman, 1996; Kanmaz, 2019; Chambers, 2019a), and lost to follow-up rate of 5%.

**Sample size for major birth defects based on varying prevalence in the SLE comparison group. The 13% is an upper end estimate from Vinet et al, the 5% is a median estimate from Gladman, 2020 and the 3% is the estimate from CDC; sample size based on prevalence within the general population (CDC, 2017). Power calculations performed in open-sourced statistical programming language R software.

*** Minimum relative risk (RR) detectable with 80% power.

^aVinet, 2012; ^bGladman, 2010; ^cCDC, 2017

Group sample sizes of 160 in each group achieve 80% power to detect a ratio of 1.9 to 2.8 when the null-hypothesized ratio is 1.0 and when background rates of major birth defects in pregnant women with SLE are used. The test statistic used is the two-sided Score test [Farrington, 1990]. The significance level of the test was targeted at 0.050. For the secondary outcome of spontaneous abortion, allowing for an elective abortion rate of 5% and a lost to follow-up rate of 5%, an estimated 180 pregnancies are expected in each cohort at the end of recruitment. Group sample sizes of 180 in each group achieve

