8.7. Data analysis

8.7.1. Essential analysis

A stepwise approach will be used for the analysis: The initial analysis will be descriptive and unadjusted. Where numbers permit, multivariable analyses will be conducted for the primary and secondary analyses to adjust for possible confounders.

Statistical methods:

A detailed SAP will be prepared and finalized prior to the conduct of any study analysis. Patient characteristics will be summarized within each cohort for the interim and final reports.

Table 6 summarizes the exposure window for each outcome.

Table 6 Summary of Exposure Window for Each Outcome

Outcome	Exposure Window
Major Birth Defects	3 months prior to LMP to the end of the 1 st trimester
Minor Birth Defects	3 months prior to LMP to the end of the 1 st trimester
Spontaneous Abortion/Miscarriage	3 months prior to LMP to prior to 20.0 weeks' gestation
Preterm Delivery	3 months prior to LMP to prior to 37.0 weeks' gestation
Other Outcomes	3 months prior to LMP to the end of the pregnancy

For the primary endpoint, the exposure of interest is belimumab exposure in the pre-conception/first trimester period. For this study, this exposure is defined as any dose from 3 months prior to the 1st day of LMP and up to 13 weeks after the 1st day of the LMP. The primary comparison will be on the rate of major birth defects between Cohort 1 and Cohort 2 among pregnancies resulting in at least one live born infant. A point estimate of the crude (i.e. unadjusted) RR of Cohort 1 versus Cohort 2, as well as its 95% confidence intervals (CIs) will be computed.

The comparison will also be carried out within each of two strata, according to whether the woman had prenatal diagnostic testing, such as level II ultrasound, amniocentesis or chorionic villus sampling, prior to enrollment in the study or not.

The same analysis will be repeated using the second numerator and denominator encompassing pregnancies ending in at least one live births, stillbirth, spontaneous abortion or elective termination, but excluding those lost-to-follow-up.

Due to the observational nature of the study, the above crude estimate of RR will be further adjusted for potential confounders, provided that there are sufficient number of events. A complete list of potential confounders will be provided in a separate table for each outcome prior to the final analysis, based on scientific knowledge including literature review. In addition, all of the following three criteria will be applied in

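### Table 4 takes its exposed N from women exposed at any time in pregnancy, but the primary analysis uses only exposure up to 13 weeks, and no allowance is made for later first exposure

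*Protocol*

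**What the plan says.** Section 8.5 plans "200 women exposed to belimumab at any time from 3 months prior to the first day of LMP through the end of pregnancy" and "200 women with SLE, unexposed to belimumab". The Cohort 1 eligibility criteria in Section 8.2.1 use the same any-time window. From 200 per cohort, Section 8.5 deducts 5% for loss to follow-up and either 10% or 15% for spontaneous and elective abortion, which leaves 170 or 160. Table 4 uses these for the primary outcome, with the footnote "N= number of pregnancies with at least one live born infant". The text adds: "Group sample sizes of 160 in each group achieve 80% power to detect a ratio of 1.9 to 2.8".

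Section 8.7.1 sets a narrower exposure for the primary outcome: "For the primary endpoint, the exposure of interest is belimumab exposure in the pre-conception/first trimester period", that is, any dose from 3 months before LMP up to 13 weeks after it. Section 8.3.1, the Cohort 1 primary endpoint in Table 2 and the first row of Table 6 agree. Second- and third-trimester exposure is considered only for selected defects for which a late effect is biologically plausible.

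**The concern.** Eligibility and the primary analysis use different exposure windows, and the sample size follows the wider one. A woman whose first dose comes after week 13 may join Cohort 1, counts toward the 200 and is carried into the 160 or 170. She is outside the Cohort 1 primary endpoint, and the Section 8.2.1 criteria and Table 2 keep her out of Cohort 2. The protocol foresees such women, since Section 8.3.1 classifies exposure by earliest trimester and defines second- and third-trimester categories. Section 8.5 makes no deduction for them.

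Two things are at stake. The detectable relative risks in Table 4 may describe a larger exposed group than the one analysed. Also, recruitment could be reported as complete at 200 while the primary comparison has fewer exposed pregnancies than its power statement assumes.

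**Working it through.** **Inputs from the protocol.** Section 8.5 and Table 4 give: 200 enrolled per cohort; live-birth fractions 0.80 and 0.85; background rates 13% and 5% (SLE) and 3% (general population); 80% power. On the test: "The test statistic used is the two-sided Score test" and "The significance level of the test was targeted at 0.050".

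**Input assumed.** The share s of Cohort 1 live-birth pregnancies first exposed after week 13. The protocol does not give it, so s = 5, 10, 20 and 30% are shown. Comparators stay at full N.

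**Step 1: the plan's N.** 200 × 0.80 = 160 and 200 × 0.85 = 170. Both reproduce, and neither contains a factor for exposure window.

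**Step 2: the plan's relative risks.** At a null ratio of 1 the score test has pooled variance under the null:

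power = Φ[(p1 − p0 − 1.96·SE0) / SE1], where

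- p1 = RR·p0, and p̄ is the pooled rate
- SE0 = √(p̄(1 − p̄)(1/n1 + 1/n0))
- SE1 = √(p1(1 − p1)/n1 + p0(1 − p0)/n0)

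At full N the RR detectable with 80% power is:

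| N per group | Background | Printed | Score test | Arcsine formula |
|---|---|---|---|---|
| 160 | 13% | 1.9 | 1.94 | 1.94 |
| 160 | 5% | 2.8 | 2.84 | 2.78 |
| 170 | 13% | 1.9 | 1.91 | 1.90 |
| 170 | 5% | 2.7 | 2.77 | 2.72 |
| 160 | 3% | 3.5 | 3.65 | 3.51 |
| 170 | 3% | 3.4 | 3.54 | 3.42 |

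The arcsine formula matches every printed value to one decimal. The named score test is higher in the 170/5% row and both 3% rows. That is a separate matter, but it means score-test power at a printed RR starts below 80% before any woman is removed.

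**Step 3: baseline at 160 per group, 5% background, RR 2.8.** p1 = 0.14, p̄ = 0.095, SE0 = 0.03278, SE1 = 0.03239. Power = Φ[(0.09 − 1.96 × 0.03278)/0.03239] = 78.7%.

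**Step 4: remove late-only women, n1 = 160(1 − s).** For s = 10%, n1 = 144 and p̄ = (144 × 0.14 + 160 × 0.05)/304 = 0.0926. SE0 = 0.03330 and SE1 = 0.03366, so power = Φ[(0.09 − 1.96 × 0.03330)/0.03366] = 76.9%. The full range is:

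| s | Exposed n | Detectable RR, 5% | Power at RR 2.8, 5% | Detectable RR, 13% | Power at RR 1.9, 13% |
|---|---|---|---|---|---|
| 0 | 160 | 2.84 | 78.7% | 1.94 | 76.5% |
| 5% | 152 | 2.86 | 77.8% | 1.96 | 75.6% |
| 10% | 144 | 2.89 | 76.9% | 1.97 | 74.5% |
| 20% | 128 | 2.96 | 74.8% | 2.00 | 72.2% |
| 30% | 112 | 3.04 | 72.3% | 2.04 | 69.3% |

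In the 170 row at 5% background, power at RR 2.7 goes from 77.4% to 75.6% (s = 10%) and 71.0% (s = 30%).

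**Step 5: the same check with the arcsine formula.** Starting from exactly 80% at the unrounded RR, power becomes 79.0, 77.8, 75.2 and 72.0% for s = 5, 10, 20 and 30%. The decline is of similar size, so it does not depend on the choice of method.

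**Step 6: an upper limit on s.** Section 8.2.1 asks for women who have been exposed. If exposure precedes enrolment, every first-trimester enrolee is inside the primary window. Section 8.5 expects about 70% to enrol then, so late-only women can come only from the other 30% or so.

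**Step 7: Table 1.** Cohort 1 is scheduled at 40 + 43 + 48 + 47 + 42 = 220, while Cohort 2 is 4 × 50 = 200. 220 × 0.80 = 176 and 220 × 0.85 = 187. Since 160/176 = 170/187 = 0.909, the extra 20 would offset a late-only share of about 9%.

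**The case against.** The best defence is that the effect is minor. At shares of 5 to 10% the detectable RR at 5% background moves by 0.02 to 0.05, no more than the gap between the score test and the formula that matches the printed table (2.84 against 2.78). Reaching 30% would need every later enrolee to be a new starter with no dose in the 3 months before LMP. Table 1's 220 could absorb about 9%. Section 8.5 presents the study as an early-warning and signal-detection exercise, the abstract makes estimates and confidence intervals the main assessments, and Section 8.9 already admits limited power for rare outcomes. No closure rule in Section 8.9.1 stops the study at 200 any-time-exposed women.

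Most of this stands and limits the size of the point. It does not remove it: Section 8.5 and Table 4 use 200, and nothing presents the extra 20 as an allowance.

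Three stronger readings are tempting and are not supported:

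- **The whole gap below 80% is due to late exposure.** It is not. The starting values of 78.7% and 76.5% come from rounding and method.
- **The 70% first-trimester figure is the share exposed in the primary window.** It describes when women enrol. A woman enrolling later may have been exposed early.
- **The abstract contradicts the body.** The abstract's "Exposure will be defined as belimumab treatment at any time during pregnancy" is the cohort-level definition and agrees with eligibility. The outcome-specific window is stated consistently in the body, so there is no basis for expecting the defect analysis to be run on any-time exposure.

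**Conclusion.** The mismatch is established from the text: the exposed N in Table 4 belongs to the any-time cohort, and the primary comparison uses a subset of it. The multiplication itself is correct; what is missing is an allowance for women first exposed after week 13. If there are none, Table 4 is unaffected.

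The size depends on a share the protocol does not give. The attributable loss is about 1 to 2 points of power at 5 to 10%, about 4 points at 20%, and 6 to 7 points at 30%. That last share is roughly the ceiling if exposure precedes enrolment. These figures apply the share to live-birth pregnancies and keep comparators at full N. A reader might infer that the primary comparison is bound to fall short. The protocol does not show that, given the unknown share and Table 1's 220. The point is worth correcting because the correction is cheap; it does not undermine the design.

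**What to change.** - In Table 4, define the exposed N as live-birth pregnancies with belimumab exposure from 3 months before LMP through 13 weeks.
- State an assumed late-only share with its basis, and restate the detectable RRs on the reduced exposed N.
- Report accrual against the target on the count of women exposed in the primary window. Late-only women still enrol and contribute to the other outcomes.
- Reconcile the 200 in Section 8.5 with the 220 in Table 1, and say whether the extra 20 are meant as this allowance.

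The cost is a revised table, a sentence or two in Section 8.5 and one more line in accrual reporting. Exposure timing is already collected at every interview (Table 3), so no new data are needed. The stated detectable RRs become slightly less favourable.

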In addition to challenges to maternal health, patients with lupus have poor obstetric outcomes compared with women without SLE, including a greater likelihood of fetal loss (approximately 3-fold increase) and a greater incidence of preterm deliveries [~40% vs. 10% among healthy women] [Clark, 2003; Clowse, 2005]. Recently a meta-analysis addressing this subject was reported [Smyth, 2010]. The proportion of pregnancies in women with SLE resulting in fetal death has been reported to be 15%-20% in European studies [Cortes-Hernandez, 2002; Julkunen, 1993] and 15%-25% in North American

studies [Clowse, 2005; Andrade, 2008], with stillbirths accounting for 2%-4% of these outcomes.

The presence of anti-phospholipid antibodies has been reported in 30%-80% of patients with SLE [Mecacci, 2009], and is associated with an increased risk of spontaneous miscarriage and poor maternal and/or fetal outcome [Cortes-Hernandez, 2002; Clark, 2007]. In prospectively examined pregnancies, with anti-Ro and anti-La antibodies in the mother, the prevalence of congenital heart block (with mortality of approximately 20%-30%) is between 1% and 5%, and rises to between 6% and 25% when another pregnancy was affected in the same mother [Jaeggi, 2010; Friedman, 2010]. Active SLE and associated comorbidities (proteinuria, anti-phospholipid syndrome, thrombocytopenia, and hypertension) have also been noted to be important predictors of fetal loss [Clowse, 2006; Cortes-Hernandez, 2002; Julkunen, 1993].

A cohort of SLE pregnancies from a single academic medical center in the US identified risk factors for fetal loss and pre-term delivery. Among pregnant patients with high SLE disease activity (Physician Global Assessment [PGA] score ≥ 2), 42% had fetal loss during the first trimester compared to 14% among women with low activity (PGA < 2). Same pattern was observed during the second (32% vs. 7%, respectively) and third trimesters (10% vs. <1%, respectively) among pregnant patients with high SLE disease activity vs. women with low activity. The combination of high disease activity, with low complement and/or anti-ds DNA auto antibodies, during the second trimester increased the risk of fetal loss and preterm delivery pregnancy outcomes [Clowse, 2011].

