Women who are interested in hearing more about the study will be referred to or will self-refer themselves to the MotherToBaby/OTIS Research Center for more information. Referrals may be by the woman's healthcare provider or by the MotherToBaby/OTIS service that the woman contacts directly. Those women who are interested and meet the study criteria as described in Section 8.2 will be invited to enroll. Women who agree to enroll will complete the oral consent process over the telephone and will then complete the initial telephone interview. Depending on the gestational timing of enrollment, subsequent telephone interviews will be conducted according to the Schedule shown in Table 5 Section 8.6.3. Follow up interviews will be conducted by telephone, and medical records for both the women and infant will be obtained and abstracted for information to validate exposures and outcomes.

The participants will reside anywhere in the U.S. or Canada. By definition, the study participants are all female, as this is a pregnancy study. The age of participants is expected to be between 18 and 45 years; however, women under the age of 18 years may enroll with parent/guardian consent, and women over the age of 45 years may also enroll.

Upon initiation of recruitment, the study is expected to continue recruitment for five years. Infant follow-up will continue for one year after the last live birth following recruitment of the last participant.

Table 1 Recruitment Timetable

	Year 1	Year 2	Year 3	Year 4	Year 5
Cohort 1 Belimumab exposed group	40	43	48	47	42
Cohort 2 Disease comparison group	--*	50	50	50	50
Exposure Case-Series	10	10	10	10	10
*Year 1: Will assess feasibility of collecting exposed group; once n=40 is attained, recruitment of comparison group will begin					

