80% power to detect a ratio of 2.1 when the null hypothesized ratio is 1.0 and when a background rate of spontaneous abortion of 10% is used. The test statistic used is the two-sided Score test [Farrington, 1990]. The significance level of the test was targeted at 0.050.

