outcomes due to lost to follow-up, pregnancy miscarriages, or terminations or stillbirths without fetal autopsy. Left truncation (late enrollment) may underestimate the risk of early pregnancy events (e.g., miscarriages, maternal death). Differences in gestational age at enrollment between exposed and reference groups could lead to biased relative risk estimates if the risk varies with gestational age. To prevent this bias, the most useful approach is to enroll subjects as early in their pregnancy as possible before outcomes can be expected and to begin follow-up of exposed and unexposed pregnancies at comparable gestational ages.

Specifically, the analysis of SAB and stillbirths is complicated by left truncation in the data, i.e., women enter the study at arbitrary times in gestation, and analyses of these outcomes must account for gestational age at enrollment. Only those women who are enrolled prior to 20.0 weeks of gestation are eligible for the analysis of SAB. Since they are not followed from gestational age zero, survival analysis methods will be used to handle left truncation, measuring time relative to enrollment, as well as right-censoring when a subject is lost-to-follow-up prior to 20.0 weeks' gestation. Left-truncated Kaplan-Meier estimate at 20.0 weeks' gestation will be used to estimate the spontaneous abortion rate in each of the cohorts with 95% CIs [Tsai, 1987]. The Cox proportional hazards regression models incorporating left truncation will be used to estimate the hazard ratio (HR) and 95% CIs of both cohorts. The individual group hazards and 95% CIs will also be presented. Stillbirth will be analyzed with a similar method.

To account for potential confounding, propensity score methods described above will be applied. In particular, regression adjustment will be used with the Cox model to obtain the adjusted HR.

The analysis of preterm delivery can also be complicated by left truncation in the data, i.e., women enter the study at arbitrary times in gestation. Only those women who are enrolled prior to 37.0 weeks of gestation are eligible for the analysis of preterm delivery. These data will be analyzed similarly to spontaneous abortion as described above using survival analysis methods, to handle possible left truncation and right-censoring.

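### Section 8.5 uses loss rates that disagree with each other and sample sizes that do not match the protocol's own analysis sets; the effect on the detectable relative risks is modest

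*Protocol*

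**What the plan says.** All of the following is in the Protocol.

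- **Birth-defect N, Section 8.5.** The base case assumes an 85% live-birth rate, "which includes a spontaneous abortion and elective abortion rate of 10"% combined plus 5% lost, giving 170 of 200. The conservative case assumes 15% combined plus 5% lost, giving 160. Table 4 prints both.
- **SAB N, Section 8.5.** After 5% elective abortion and 5% lost, "an estimated 180 pregnancies are expected in each cohort at the end of recruitment". The detectable ratio is 2.1, "when a background rate of spontaneous abortion of 10% is used". The test named for both outcomes is the two-sided score test.
- **Enrolment timing.** Section 8.5 says "the expected proportion of women to enroll in first trimester is approximately 70"%, with mean enrolment at 7-10 weeks. Table 5 allows enrolment at any time in pregnancy.
- **SAB analysis set, Section 8.7.1.** "Only those women who are enrolled prior to 20.0 weeks of gestation are eligible for the analysis of SAB". Table 2 adds exposure before 20 weeks (Cohort 1) and at least one follow-up contact.
- **Primary analysis set, Section 8.7.1.** For the primary endpoint, "this exposure is defined as any dose from 3 months prior to the 1st day of LMP and up to 13 weeks" after LMP. The 200 in Section 8.5 counts exposure at any time up to the end of pregnancy.
- **Recruitment, Table 1 (Section 8.2.2).** The row "Cohort 1 Belimumab exposed group" reads 40, 43, 48, 47 and 42. Section 8.9.1 speaks of about 40 exposed women a year over five years.

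**The concern.** One section uses two incompatible assumptions about early loss. SAB of 10% plus elective abortion of 5% is 15%, which contradicts the 10% combined rate behind the 170 rows. Separately, neither the 180 nor the 160/170 is the number of women who will enter the analysis being sized. The protocol's rules on gestational age at enrolment, on exposure window and on live birth all remove women whom Section 8.5 leaves in.

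This matters because the study is presented as an early-warning system. If it finds nothing, readers will quote the 80% power statements to say what size of effect has been ruled out. Those statements should rest on consistent inputs and on the right denominators.

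**Working it through.** **Method.** Two-sided α = 0.05, score test at a null ratio of 1 (pooled variance):

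power = Φ{ [|p₂ − p₁| − 1.96·√(p̄(1−p̄)(1/n₁+1/n₂))] / √(p₁(1−p₁)/n₁ + p₂(1−p₂)/n₂) }

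Here p₁ is the comparison rate, p₂ = RR × p₁, and p̄ is the pooled rate. The detectable RR is the value that gives power 0.80.

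**1. Reproducing the plan**

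- Counts: 200 × 0.85 = 170; 200 × 0.80 = 160; 200 × 0.90 = 180. All correct as arithmetic.
- SAB, n = 180, p₁ = 0.10, RR 2.1: p₂ = 0.21 and p̄ = 0.155. The null SE is √(2 × 0.155 × 0.845/180) = 0.0381. The alternative SE is √((0.09 + 0.1659)/180) = 0.0377. Then (0.11 − 1.96 × 0.0381)/0.0377 = 0.93, so power is 82.5%. The detectable RR is 2.06, printed as 2.1.
- Table 4:

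| N per group | Background | Printed RR | Score test | Arcsine formula |
|---|---|---|---|---|
| 160 | 13% | 1.9 | 1.94 | 1.94 |
| 160 | 5% | 2.8 | 2.84 | 2.78 |
| 170 | 13% | 1.9 | 1.91 | 1.90 |
| 170 | 5% | 2.7 | 2.77 | 2.72 |
| 160 | 3% | 3.5 | 3.65 | 3.51 |
| 170 | 3% | 3.4 | 3.54 | 3.42 |

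The arcsine formula matches all six printed values. The score test that the text names is higher in the 170/5% row and in both 3% rows.

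**2. One set of loss rates.** SAB 10% + elective 5% + lost 5% = 20%, and 200 × 0.80 = 160. The 170 rows therefore conflict with the SAB calculation. In printed values the move from 170 to 160 is 2.7 to 2.8 at 5%, 3.4 to 3.5 at 3%, and none at 13%.

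**3. SAB: enrolled before 20.0 weeks.** The protocol does not give the share enrolling later, so it is assumed here:

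| Excluded (assumed) | N per cohort | Detectable RR | Power at 2.1 |
|---|---|---|---|
| 0% | 180 | 2.06 | 82.5% |
| 5% | 171 | 2.09 | 80.5% |
| 10% | 162 | 2.13 | 78.4% |
| 15% | 153 | 2.16 | 76.0% |

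Power at 2.1 drops below 80% once N is under 169, that is, once more than 11 of the 180 (about 6%) are ineligible.

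**4. Birth defects: exposure window and stillbirth.** Score test, 5% background, each change taken alone from the 160/160 reference of 2.84:

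- First exposure after week 13 in 10% or 20% of Cohort 1 (assumed): 144 or 128 exposed against 160, giving RR 2.89 or 2.96.
- Stillbirth in 2% or 4% of pregnancies: 200 × 0.78 = 156 or 200 × 0.76 = 152 per cohort, giving RR 2.87 or 2.90. Section 6.1 gives 2-4% with an unclear denominator, so reading it as a share of pregnancies is an assumption.

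**5. Recruitment.** 40 + 43 + 48 + 47 + 42 = 220, against 200 in Section 8.5 and about 40 × 5 = 200 in Section 8.9.1. With 220 × 0.80 = 176 exposed against 160 comparators, the score-test RR at 5% is 2.79. This works in the study's favour.

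**The case against.** The strongest reply is that the conflict is narrow. The 180 and the 160 rest on the same rates. Section 8.5 offers 170 and 160 as alternative scenarios, and its prose power statement for birth defects uses only 160. Elective terminations and losses to follow-up can contribute censored time in the planned SAB survival analysis, so removing them entirely is cautious. Section 8.5 describes signal detection, and Section 8.9 admits limited power. All of this stands and keeps the size small. It does not remove the contradiction or supply the missing deductions.

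Several stronger readings are tempting but unsupported:

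- **All 30% who enrol after the first trimester are lost to the SAB analysis.** For an overall mean of 10 weeks, the other 70% would have to average at most (10 − 0.3 × 20)/0.7 = 5.7 weeks. Even 15% excluded, with another 15% enrolling just after week 13, needs a first-trimester average of at most 7.2 weeks, so 15% is already towards the upper end.
- **SAB is really 5%.** No section says so. It comes only from subtracting one scenario's rate from another's.
- **Live births should be cut by the fetal-death range of "and 15%-25% in North American" studies.** That range in Section 6.1 covers SLE pregnancies generally. Section 8.9 says the highest SAB risk precedes typical enrolment, so the range is not post-enrolment loss.
- **Weighting inflates the variance by a known amount.** The protocol gives nothing from which to size this, and it also plans a crude RR.

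**Conclusion.** Section 8.5 is wrong as written, by a modest amount. The loss-rate conflict is established from the text alone; it affects only the 170 rows and moves the printed RR by at most 0.1. The mismatch with the analysis sets is also established, and each omitted deduction pushes the detectable RR upwards. How far depends on shares that the protocol does not state. Under the assumptions shown, the SAB ratio is 2.09-2.16 rather than 2.06, and the birth-defect RR at a 5% background is 2.87-2.96 rather than 2.84, taking one deduction at a time.

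A reader might infer that the planned analyses simply do not have the stated power. The documents do not support that without conditions: the SAB figure has slack down to 169 per cohort, and 220 exposed women would offset part of the loss. Part of the gap between score-test results and the printed Table 4 comes from the formula, not from N.

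**What to change.** Revise Section 8.5 and Table 4, leaving enrolment as it is:

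1. Use one set of rates for SAB, elective abortion, stillbirth and loss to follow-up throughout.
2. Drop the 170 rows, or label them as a scenario that conflicts with the 10% SAB assumption.
3. Base the SAB N on women expected to enrol before 20.0 weeks, and the birth-defect N on live births with preconception or first-trimester exposure in Cohort 1. State the assumed shares.
4. Recompute every detectable RR with the score test that the text names.
5. Reconcile the 220 in Table 1 with the 200 in Section 8.5.

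The cost is a recalculated table and a few sentences. No extra participants are needed, and some stated RRs become slightly less favourable.
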